# 1.1.2 Responsibilities

The responsibilities of these individuals are described briefly here:

PI and co-PIs are responsible for ensuring the proper conduct of the study clinic site including recruitment as specified in the protocol and accurate collection of the data. Other specific duties include:

- a. Obtaining and maintaining IRB approval and training for study personnel
- b. Obtaining sufficient study areas for study personnel to interview patients and perform study procedures, including storage of study medication and other study supplies.
- c. Participate in study- related meetings or conference calls
- d. Familiarity and training for REDCap based data entry system by appropriate staff.
- e. Screen potential participants for eligibility and consent them. It is important to ensure the patient's primary obstetric provider agrees to follow the study treatment protocol during pregnancy.
- f. Randomize per protocol to intervention arms both arms to receive medication
- g. Follow participants during the antepartum, delivery and 6 (4-12) weeks postpartum periods: with labs as indicated in the protocol and with pre- and post-intervention surveys to monitor patient symptoms and adverse effects

- h. Facilitate collection of labs at 24-28 weeks gestation (preferred window, but may collect up to 34 complete weeks), labs at 4 and 8 weeks post-initiation of pill for standard group and post-treatment of intravenous iron in the active group and delivery.
- i. Trained research staff will conduct research data abstraction from patient medical records, and conduct participant interviews, pill counts, and other direct participant contact as required by the protocol. Research staff at CTRU, will undergo training to ascertain response to severe adverse outcomes, specifically identification of hypersensitivity reactions to intravenous iron.
- j. Investigators will participate in blinded review of outcomes in order to confirm the primary and other key outcomes.
- k. Maternal outcomes will be ascertained through 6 weeks including a postpartum visit in this window. If unscheduled visits occurred at another facility, obtain medical records release (if one has not already been obtained) to order hospital visit records.

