# **6. RANDOMIZATION AND BASELINE VISIT PROCEDURES**

In participants with IDA prior to 24 weeks' gestation, they can still be included in the study if they meet the inclusion criteria at 24 weeks gestation/ enrollment time frame. If IDA is a new diagnosis at the time of 24-28 weeks gestation, patients meeting the inclusion criteria be included.

In both groups, prenatal data will be obtained at the randomization visit. The randomization visit should occur with timing of lab results availability and prenatal visit if applicable.

Randomization may occur upon confirmation that all exclusion/inclusion criteria are satisfied and after verification of participant consent and HIPAA authorization. Of particular importance, careful consideration will be given the patient's prior history and medications to determine final eligibility and the appropriate study algorithm to follow (see below). Study staff will also verify participant contact information and obtain a Release of Information.

The MFM Research team will review the following before randomization:

- Complete review of all exclusion and inclusion criteria
- Informed consent obtained
- Iron studies and baseline labs to confirm eligibility
- Pre-intervention survey to assess symptoms

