#### After randomization:

- Provide medication and instructions based on the treatment arm randomized to
- Provide the group algorithm to both patient and provider.

Once the participant is randomized, the treatment algorithms will be conspicuously placed in the patient's medical record (whether electronic or paper medical record is utilized) such that providers will be aware of treatment plan at all times.

In both groups, serial CBC follow up and survey for symptoms will be assessed. Baseline data consisting gestational age of pregnancy, body mass index, pre-pregnancy weight and other prenatal data including baseline BP at the randomization visit will be included. Patients will be assigned to treatment groups by a concealed randomization allocation sequence using REDCap.

The categories of patients randomized:

Patients consenting to the study will be randomized 1:1 to two treatment groups

Group 1: Patients randomized to the IV iron group will receive treatment as follows:

- Women with Hgb 9-10.9 g/dL will receive one dose of 510 mg IV ferumoxytol
- Women with Hg 7-8.9 d/dL will receive two doses of ferumoxytol 510 mg 3-8 days apart for a maximum of dose of 1020 mg (see **Figure 2**).
- Patients will receive 650mg of Tylenol prior to initiation of the infusion
- The ferumoxytol is administered as an infusion for approximately 15-30 minutes. Patients will receive the IV iron at Stanford's Clinical and Translational Research Unit (CTRU) outpatient clinics with vitals collected before infusion and monitoring for 30minutes after infusion. Alternatively, patients who are admitted to the antepartum unit may receive the infusion inpatient.

For the IV iron group, follow up labs will be performed at 4 and 8 weeks after completion of infusion/s;

Group 2: The standard of care oral iron group will be prescribed 1-2 ferrous sulfate 325 mg tablets to be taken by mouth **every other day** until delivery. Dosage will be as follows for standardization:

- one ferrous sulfate tablet every other day if Hg 9-10.9 g/dL, and
- two tablets once every other day if Hg 7-8.9 g/dL.
- Oral medications will be dispensed by the CTRU or by the Outpatient Investigational Pharmacy (final confirmation pending contracts)
- Follow up labs will be drawn for both groups. For the oral iron group, it will be drawn 4- and 8-weeks post initiation of treatment

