# 12.3 Analyses

We will conduct an intent-to-treat analysis to compare the primary and secondary outcomes between the treatment arms. The primary outcome is the mean change in hemoglobin in oral vs IV iron over 4 weeks as well mean change in hemoglobin pre delivery. The primary outcome will be assessed using t-tests. Baseline characteristics between the groups will be compared using t-tests and chi-square tests. If there is an imbalance between the treatment arms, we will use multivariable regression modeling. Differences will be considered statistically significant at P<0.05.

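### Section 12.3 leaves baseline adjustment conditional and unspecified; a prespecified model with baseline hemoglobin costs almost nothing and gains nil to moderate power

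*Combined protocol and SAP*

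**What the plan says.** Section 12.3 defines the primary outcome as mean change in hemoglobin, over 4 weeks and before delivery, and states: "The primary outcome will be assessed using t-tests". It continues: "Baseline characteristics between the groups will be compared using t-tests and chi-square tests", and then: "If there is an imbalance between the treatment arms, we will use multivariable regression modeling". The significance level is P<0.05.

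No section lists the characteristics to be compared, names the covariates of the regression, says whether baseline hemoglobin is among them, or says whether the regression replaces or supplements the t-test. The threshold for imbalance is not stated either, although P<0.05 on the baseline tests is a natural reading.

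Baseline hemoglobin is known for every woman before randomization, because section 6 requires "Iron studies and baseline labs to confirm eligibility". It also sets the dose band in both arms (section 6, After randomization: "Women with Hgb 9-10.9 g/dL will receive one dose of 510 mg IV ferumoxytol"; "one ferrous sulfate tablet every other day if Hg 9-10.9 g/dL"). No stratification of the randomization by hemoglobin is described.

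**The concern.** Baseline hemoglobin is one component of the change score, defines eligibility and sets dose, so it is the obvious covariate for both hemoglobin outcomes. Two things are at stake.

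- **Precision.** A model that always includes baseline hemoglobin usually estimates the treatment difference more precisely than the t-test on change. A rule that adjusts only after an observed imbalance leaves most trials with the unadjusted analysis.
- **Prespecification.** The trial is open-label (section 4.1), and section 1.1.1 leaves final analysis decisions to the steering committee. With covariates and status unstated, there are two candidate primary results, and nothing in the plan fixes which one counts.

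**Working it through.** **The plan's own figure.** Section 12.3 gives no number on this point. The 32 per arm in section 12.2 is for a proportion outcome with no proportions stated. It can only be inverted (25 / 0.8 = 31.25, rounded up to 32), and many pairs fit, for example about 0.80 vs 0.365 or 0.70 vs 0.26. It is neither confirmed nor refuted, and the check below does not depend on it.

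**Inputs from the documents.** 40 per arm (section 4.3) less 20% drop-out (section 12.2) leaves 40 × 0.8 = 32 evaluable per arm. The expected differences are 0.8 − 0.5 = 0.3 g/dL at 4 weeks and 1.5 − 1.0 = 0.5 g/dL at birth admission (section 3.1), and 1.5 g/dL in section 12.1. P<0.05 is taken as two-sided.

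**Assumed inputs.** The documents give no SD and no baseline-to-follow-up correlation. I take follow-up SD s1 = 1.0 and r = 0.3, 0.5, 0.7. Entry at 7-10.9 g/dL limits the baseline SD s0: even a flat distribution over that range has SD 3.9/√12 = 1.13, and a peaked one has less. I use s0 = 0.6, 0.7 and 0.86, with 1.0 as an upper case.

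**Formulas.**
- Variance of change: s0² + s1² − 2·r·s0·s1.
- Residual variance with baseline as covariate: s1²(1 − r²).
- The difference between the two is (s0 − r·s1)², which is zero when the within-arm slope of follow-up on baseline, r·s1/s0, equals 1.
- Price of estimating the slope: variance × (1 + 1/(64 − 4)) = 1.017, about 0.9% on the width of the confidence interval.
- Power: noncentral t with 62 df (t-test) or 61 df (adjusted).

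**One case in full** (s0 = 0.86, r = 0.3, difference 0.5):
- t-test: variance 0.7396 + 1 − 0.516 = 1.2236; SE = √(2 × 1.2236/32) = 0.277; power 43%.
- Adjusted: variance 0.91; SE = √(2 × 0.91 × 1.017/32) = 0.240; power 53%.

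**Power at 0.5 g/dL, t-test to adjusted model:**

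| Baseline SD | r = 0.3 | r = 0.5 | r = 0.7 |
|---|---|---|---|
| 0.6 | 50 to 53% | 62 to 62% | 78 to 78% |
| 0.7 | 48 to 53% | 60 to 62% | 79 to 78% |
| 0.86 | 43 to 53% | 56 to 62% | 77 to 78% |
| 1.0 (upper case) | 38 to 53% | 50 to 62% | 72 to 78% |

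At s0 = 0.86 the unrounded gains are about 11, 6 and 1 points. The worst case is s0 = 0.7 with r = 0.7, where the slope is exactly 1: 78.7% to 78.0%. At 0.3 g/dL the gain is 0 to about 5 points for s0 up to 0.86, and 6 at s0 = 1.0. At 1.5 g/dL both analyses have about 100% power.

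**The conditional rule**, simulated with 60,000 trials per scenario and adjusting only if the baseline-hemoglobin t-test has P<0.05:
- It fires in about 5% of trials, and its power stays within 1 point of the plain t-test.
- Type I error is about 5% for the t-test, about 5% for the adjusted model and 4-5% for the rule.
- If a trial counts as positive when either model is significant, type I error is about 5.5-8%, highest where baseline SD is large and correlation low.

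**The case against.** The strongest reply is that nothing here is an error. The t-test on change is valid under randomization, the rule does not inflate type I error, section 3.1 calls the trial a pilot, and at the 1.5 g/dL difference in section 12.1 the choice of model makes no difference. All of that stands. It limits the point to precision and prespecification.

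Second, the gain may be nil. That also stands: with baseline SD 0.6-0.7 and r of 0.5 or more it is 0 to 2 points, or a loss of under 1. The 15-point gain needs a baseline SD of 1.0, near the top of what the entry range allows.

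Third, the trigger can reasonably be read as P<0.05 on the baseline tests, and an imbalance in any characteristic might bring in a model that includes hemoglobin. This is partly right. With five independent characteristics tested, at least one is flagged in 1 − 0.95⁵ = 23% of trials. If hemoglobin then always entered, the rule would recover roughly 0.23 × 11, or 2 to 3, of the 11 points. Covariates and status would still be open.

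A reader might go further and infer that the planned analysis is biased, that the two-step rule itself inflates type I error, or that the investigators mean to report the better of two results. The documents support none of these. The 5.5-8% applies only if the choice is made on the results. The plan does not propose that; it only fails to exclude it.

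**Conclusion.** The point holds as a low-cost improvement, not as a flaw that invalidates the analysis. Section 12.3 leaves the covariates and the status of its adjusted analysis open, and its conditional rule captures almost none of the precision available from a covariate that is already measured. Under the stated assumptions, routine adjustment changes power at 0.5 g/dL by about 0 to +11 points, with +15 as the upper case and about −1 at worst. The textual finding is firm. The size of the gain is not, because it depends on SDs and a correlation that the documents do not give.

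It would also be wrong to infer that adjustment rescues the power. At 0.5 g/dL the adjusted model reaches only 53-78% in these scenarios, below the 90% that section 12.2 states for a different outcome.

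**What to change.** In section 12.3, make the primary analysis of each hemoglobin outcome (4-week and pre-delivery) a linear model with treatment and continuous baseline hemoglobin, fitted whatever the observed balance, and report the adjusted mean difference with its 95% confidence interval. The endpoint can stay as change: with baseline in the model, analysing change or follow-up value gives the same treatment estimate. Delete the imbalance trigger, so that baseline comparisons are descriptive and play no part in choosing the model. Keep the unadjusted t-test as a named sensitivity analysis.

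The cost is about two sentences, no new data, one degree of freedom and at most about 1 point of power. This settles the choice of model only; having two primary time points is a separate matter.

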# Primary safety outcome:

- O Rates of adverse events
- o Compliance with medication
- o Severe neonatal composite morbidity
- o Severe maternal morbidity

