# 2. STUDY INFORMATION

#### 2.1 Study Rationale

Iron deficiency is the most common cause of anemia in pregnancy in the United States (Mei). Our study will add key evidence to improve the management of antepartum IDA in late pregnancy, when women are at particularly high risk for poor outcomes. Our study will also assess previously unstudied outcomes, notably blood transfusion.

Rationale for change in intravenous iron

The initial proposal aimed to conduct a prospective open label randomized clinical trial comparing standard of care (SOC) oral ferrous sulfate to IV FCM for the treatment of anemia in pregnancy. FCM was the IV iron formulation of choice based on a FER-ASAP clinical trial and meta-analysis supporting safety of iv irons in pregnancy . It also has required less time per infusion (30min) and max course of 2 doses. As highlighted by the reviewers, hypophosphatemia is an increasing concern noted in studies of nonpregnant populations. Further review of previously

existing study protocols shows that serum phosphate was not assessed in initial trials evaluating safety in pregnant women. Huang et al is the only study that reports the rate of hypophosphatemia in a cohort of 20 pregnant women, one of which developed clinically relevant hypophosphatemia. The expertise of Stanford faculty [name], a co-author in "Randomized Clinical trial of IV iron induced hypophosphatemia", graciously provided further assistance and helped to contextualize previous research experience with CKD patients. As a precaution, this study proposal has been significantly modified to exclude the use of FCM.

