# Information adapted from package insert

Black Box warning on label: "Serious hypersensitivity reactions, (some fatal), including anaphylaxis may occur, presenting with cardiac/cardiorespiratory arrest, clinically significant hypotension, syncope, or unresponsiveness even in patients who previously tolerated ferumoxytol. Infuse over ≥15 minutes and have equipment for resuscitation and trained personnel experienced in handling emergencies immediately available during use. Monitor patients for signs/symptoms of hypersensitivity reactions, including blood pressure and pulse during and ≥30 minutes (until clinically stable) following administration. Other hypersensitivity reactions have also occurred (pruritus, rash, urticaria, wheezing). Patients with multiple drug allergies may have greater risk of anaphylaxis; elderly patients with multiple or serious comorbidities who develop hypersensitivity and/or hypotension after ferumoxytol may be at greater risk for serious adverse events."

Fatal and serious hypersensitivity reactions including anaphylaxis have occurred in patients receiving ferumoxytol in less than 1%. Initial symptoms may include hypotension, syncope. Unresponsiveness, cardiac/cardiorespiratory arrest.

Hypersensitivity reactions have occurred in patients in whom a previous ferumoxytol dose was tolerated. Other adverse reactions potentially associated with hypersensitivity have occurred (pruritus, rash, urticarial reaction and wheezing). Patients with a history of multiple drug allergies may have a greater risk of anaphylaxis with parenteral iron products.

Excessive therapy with parenteral iron can lead to excess storage of iron with the possibility of iatrogenic hemosiderosis.

Administration of ferumoxytol may transiently affect the diagnostic ability of magnetic resonance imaging. Alteration of MR imaging studies may persist for up to 3 months following the last ferumoxytol dose. The most common serious AEs reported in ferumoxytol-treated

patients were syncope, gastroenteritis, seizure, pneumonia, hemorrhagic anemia, and acute kidney injury.

A separate protocol is referenced below for the management of hypersensitivity reactions.

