# 4.3 End of Study Definition

The study will be complete once enrollment has been completed. The goal is 80 patients with 40 in each arm.

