#### 12. STATISTICAL ANALYSIS

#### 12.1 Statistical Considerations

Efficacy Endpoint(s): The primary outcome for this study is to assess the delta in hemoglobin pre and post intervention in both treatment groups. Our hypothesis is that the rate of increase of intravenous iron will be approximately 1.5g/dL higher in the IV iron cohort versus the oral iron cohort

Secondary Efficacy Endpoint(s): The secondary outcomes for this study include the following:

- correction of anemia at the time of birth hospitalization,
- rates of blood transfusion,

- neonatal outcomes such as APGARs and NICU admissions
- maternal/neonatal infection
- mode of delivery (NTSV)
- infant birth weight

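### Section 12.3 applies one unadjusted P<0.05 rule to every between-arm difference: false-positive risk builds up across 7 to 14 secondary and safety outcomes, and for rare events at 40 per arm non-significance says almost nothing

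*Combined protocol and SAP*

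**What the plan says.** Section 12.3 sets the scope: "We will conduct an intent-to-treat analysis to compare the primary and secondary outcomes between the treatment arms". It defines the primary outcome as the "mean change in hemoglobin in oral vs IV iron over 4 weeks as well mean change in hemoglobin pre delivery", to be compared by t-test, and ends with "Differences will be considered statistically significant at P<0.05". That last sentence is not limited to the primary outcome. Section 12.3 names no test for binary secondary outcomes; chi-square appears only for baseline characteristics.

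The other outcomes sit in three partly overlapping lists.

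- Section 12.1, introduced by "Secondary Efficacy Endpoint(s): The secondary outcomes for this study include the following": correction of anemia, transfusion, Apgar scores, NICU admission, maternal/neonatal infection, mode of delivery and birth weight.
- Section 3.2: discontinuation, adverse events, transfusion and symptoms.
- The synopsis list headed as primary safety outcome: adverse events, compliance, "Severe neonatal composite morbidity" and severe maternal morbidity.

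On size, section 4.3 states "The goal is 80 patients with 40 in each arm". On expectations for rare events, section 2.1 says "Our study will also assess previously unstudied outcomes, notably blood transfusion", and the package-insert text in section 2.3.2 says that serious hypersensitivity reactions "have occurred in patients receiving ferumoxytol in less than 1"%.

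**The concern.** A single significance threshold is being asked to do two jobs, and it suits neither at this size.

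For common or continuous outcomes (birth weight, symptoms, mode of delivery), many tests at 0.05 make it fairly likely that something crosses the line by chance. Nothing in the plan tells the analyst or reader how to discount that.

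For rare outcomes (transfusion, severe morbidity, serious reactions), the test will almost always be non-significant whatever the truth, and the plan provides no interval to show how much harm or benefit remains possible. Section 2.1 presents transfusion as a notable outcome of the study, so the reading of that comparison matters.

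This is separate from the two hemoglobin comparisons named as primary, which raise their own multiplicity question.

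**Working it through.** **Inputs**

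- Significance level 0.05, from section 12.3. Sidedness is not stated there; two-sided is assumed.
- 40 women per arm, from section 4.3. With the 20% drop-out of section 12.2, 40 × 0.8 = 32 would be evaluable.
- Outcome counts from the three lists. Section 12.1 gives 7, or 8 if maternal and neonatal infection are counted separately. Section 3.2 adds three (discontinuation, adverse events, symptoms). The synopsis adds three more (compliance, severe neonatal morbidity, severe maternal morbidity). Total 7 + 3 + 3 = 13, or 14.
- Event rates for secondary outcomes are not given. Those used below are assumptions.

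**The plan's own figure.** The plan states no family-wise error rate and no power for any safety outcome. Its one sizing figure, 32 per arm in section 12.2, cannot be reproduced because the two proportions behind it are not given. Nothing below depends on it.

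**1. Chance of at least one false positive.** With k independent tests and every null true, this is 1 − 0.95^k.

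| Outcomes counted | k | Chance of at least one P<0.05 |
|---|---|---|
| Section 12.1, infection pooled | 7 | 30.2% |
| Section 12.1, infection split | 8 | 33.7% |
| Merged lists, infection pooled | 13 | 48.7% |
| Merged lists, infection split | 14 | 51.2% |

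These are near-ceiling values, for two reasons.

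- *Correlation.* For 14 tests with equal correlation of 0.1, 0.3, 0.5 or 0.7, simulation gives 50%, 44%, 35% or 25%.
- *Discreteness.* A test on a rare event cannot use up its 5%. At 40 per arm and a true rate of 2% in both arms, the actual error rate is 0.01% for Fisher and 0.7% for uncorrected chi-square; at 5% it is 0.4% and 4.3%. An assumed mix of 3 continuous and 11 binary outcomes, with rates from 2% to 30%, gives about 28% with Fisher and 46% with chi-square.

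**2. What a non-significant result means for rare events.** Exact power at 40 per arm, assumed rates:

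| Rates | Fisher | Uncorrected chi-square |
|---|---|---|
| 10% vs 5% | 4% | 15% |
| 10% vs 2% | 11% | 34% |
| 20% vs 5% | 41% | 57% |

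A split of 5 events against 0 gives Fisher P = 0.055, and 6 against 0 gives P = 0.026. Uncorrected chi-square gives P = 0.021 for 5 against 0. The label attached to the same data would therefore turn on a test that the plan does not name.

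**3. What a zero count leaves open.** The upper 95% limit for 0 events in n women is 1 − 0.05^(1/n) one-sided or 1 − 0.025^(1/n) two-sided.

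- n = 40: 7.2% or 8.8%.
- n = 32: 8.9% or 10.9%.

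A reaction with a true rate of 1% would go unseen in 40 infused women with probability 0.99^40 = 67%. With 0 events in both arms of 40, the 95% (Newcombe) interval for the difference is ±8.8 percentage points; with 2 in each arm it is ±12.1.

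**The case against.** Several points on the other side are sound.

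- *The high error figure is a ceiling.* It needs 14 independent tests, each using its full 5%, with every null true. It also needs three lists to be merged and one item split. Outcomes too rare to reveal harm add almost no false positives. This stands, and it is why the figure is given as a range.
- *A significant secondary result need not be chance.* A reader might infer that such a result is probably spurious. The documents do not support that. The family-wise rate is the probability of at least one hit when nothing differs, not the probability that a given hit is false. Section 2.2 reports side effects in more than 70% of women on oral iron and discontinuation in about half, and section 3.1 expects a better hemoglobin response to IV iron, so some differences may well be real. At an assumed 50% versus 15%, Fisher power with 40 per arm is about 90%.
- *The P-value is not the only safety provision.* Sections 10 to 10.2 provide event reporting, IRB notification and DSMB review, none of which uses a P-value. A reader might infer that P<0.05 is the sole safety criterion; it is not. It is only the sole stated rule for the between-arm comparison. The zero-event limit for infusion reactions is likewise a single-arm precision figure and does not arise from that rule.
- *The plan never says that non-significance shows safety.* Correct. Section 3.1 calls the trial a pilot, and section 12.2 says a much larger sample is planned for rare secondary outcomes. That acknowledges the limit, but gives no size for the larger sample and leaves the P<0.05 rule in force for these outcomes here.
- *Not every listed outcome is a like-for-like test, or clearly secondary.* Section 13 measures compliance by pill count in one arm and infusion log in the other. Correction of anemia appears under the primary composite in the synopsis and is the basis of the sample size in section 12.2, yet is secondary in section 12.1. The fix has to deal with this.

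What remains is the absence of any hierarchy, adjustment, exploratory label or interval rule.

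**Conclusion.** The concern holds in a limited form. Section 12.3 applies one unadjusted threshold to all between-arm differences. The resulting chance of at least one false positive is 30–34% for the section 12.1 outcomes and at most about 50% for the merged lists. Both figures assume independent tests and no true effect, and correlation or rarity lowers them; in the settings examined, the merged-list figure ran from about 25% to 50%.

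For rare binary outcomes, a non-significant P-value at 40 per arm carries almost no information. That conclusion rests on assumed event rates, but low power persists with either common test at 10% versus 5% or 10% versus 2%. The zero-event limits need no rate assumption.

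The documents do not support a claim that chance findings are as likely as not, or that the sponsor intends to declare safety from a null result. The gap is that section 12.3 supplies no other way to read these comparisons.

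**What to change.** 1. Reconcile the status of correction of anemia across the synopsis, section 12.1 and section 12.2, and name the primary analysis. Until that is done, limiting significance language to the primary analysis has no clear meaning and could label as exploratory the outcome on which the trial was sized.
2. In section 12.3, limit the phrase statistically significant to the designated primary analysis.
3. Report all other secondary and safety outcomes as between-arm differences with 95% confidence intervals, using exact methods for rare binary events, and label them exploratory.
4. Where an arm has zero events, state the upper 95% limit that the count leaves open.

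This is a change of wording, with no added participants, visits or data. The downside is that no confirmatory claim can be made for a secondary outcome.
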